## **8.1 Statistical analysis of the primary efficacy variable**

The primary efficacy variable described in Section 2.2.1.1 will be analyzed using the logit-transformed iRODS score to compute the change from Baseline to Week 13 (Day 85).

### **8.1.1 Derivations of primary efficacy variable**

The iRODS is a linearly weighted patient-reported outcome measure (questionnaire) that specifically captures activity and social participation limitations in patients with CIDP. The iRODS scale was constructed based on the World Health Organization (WHO) International Classification of Functioning, Disability and Health, literature search, and patient interviews.

All 24 items of iRODS meet Rasch model expectations. The questionnaire consists of 24 items (including eating, taking a shower, walking a flight of stairs, standing for hours, etc.) and assesses a patient's perception of their ability to perform daily and social activities. Patients have 3 response options: 0=impossible to perform; 1=performed with difficulty; and 2=easily performed, performed without difficulty.

The raw sum scores of iRODS (range 0 to 48) is an ordinal scale and does not allow for easy interpretation of differences. For this reason, the ordinal scale will be translated to log odds units (logits) scale using the nomogram in Section 13.1, placing patients' estimates on the same logit scale. The primary analysis and iRODS summary will be performed on logit locations. For easier interpretation the person locations (logits) will be translated to centile metric scores changing from 0 (most severe activity and social participation restrictions) to 100 (no activity and social participation limitations). Both transformed and untransformed data will be provided in tables and key results will be presented in transformed and original units to aid interpretation based on the raw scores.

### **8.1.2 Analysis of the primary efficacy variable**

The primary analysis will be based on a MMRM analysis (fixed effect terms: treatment group, the Baseline location iRODS score, route of administration of prior Ig therapy (as captured in the eCRF Prior and Concomitant Medication form), assessment week (at pre-specified levels determined by the visit schedule) and the treatment by week interaction and study participant as a random effect, and utilize an unstructured covariance matrix).

The Kenward-Roger approximation will be used to estimate denominator degrees of freedom. In case of non-convergence, the model will be fitted using the following covariance matrices until convergence is met: Heterogeneous Toeplitz, Heterogeneous autoregressive, Toeplitz, Autoregressive.

SAS proc MIXED will be used:

- a. Subject ID, treatment group, prior Ig therapy and visit will be set as classes

---

- b. The model will be specified with covariates baseline score, treatment group, prior Ig therapy, visit and treatment\*visit
- c. The repetition variable is visit.
- d. Subject ID is set as random factor.
- e. Covariance structure as described above.
- f. LS means, differences and confidence limits for treatment\*visit are requested.

An estimate for the placebo-adjusted treatment effect with 90% CI will be produced on logit location scale, on the raw scores as well as centile metric scores.

Imputation rules are given in Section 4.2.1.

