## **14.3 Planned efficacy analyses**

### **14.3.1 Analysis of the primary efficacy variable**

The primary efficacy variable is the change from Baseline to Week 13 (Day 85) in the iRODS score.

The primary analysis of the primary variable will be based on a mixed model repeated measures (MMRM) analysis of covariance (ANCOVA) that includes terms for treatment group, the Baseline iRODS score, the prior Ig therapy, and the interaction between treatment group and week. The model will define subject as a random effect and utilize an unstructured covariance pattern.

An estimate for the placebo-adjusted treatment effect with a 2-sided 90% confidence interval (CI) will be produced.

For subjects who prematurely withdraw for any reason before Week 13 (Day 85), data collected during the PEOT Visit will be used to impute iRODS at the next visit. Since the analysis is based on the MMRM approach, visits beyond the PEOT Visit will not be imputed.

Different sensitivity analyses to evaluate the effect of missing observations on the primary analysis findings will be done. The first sensitivity analysis will be performed in the same way as the primary analysis, however for the PPS. A further analysis will utilize the last observation carried forward (LOCF) approach; missing values will be replaced by the last observed post-Baseline value of the variable and the analysis will be performed on the resulting dataset. An additional sensitivity analysis will be performed excluding any subject who received a mean dose more than  $\pm 10\%$  from the intended dose.

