Values and changes from Baseline in adjusted INCAT score will be summarized by treatment group and for all participants and listed by treatment group at each scheduled assessment during the Treatment and Observation Period. For the change from Baseline at each scheduled assessment during the Treatment and Observation Period, treatment differences will be compared using the same MMRM analysis as for the primary endpoint, with the fixed categorical effects of treatment group, assessment week (at pre-specified levels determined by the visit schedule), the treatment by week interaction and the route of administration of prior Ig therapy, as well as continuous fixed covariate of the Baseline value and participant as a random effect. Analyses will be performed for the FAS utilizing the observed cases and repeated for the PPS.

INCAT score measurements will be listed by treatment group.

The statistical methods applied to CIDP relapse (adjusted INCAT) and time to CIDP relapse (adjusted INCAT) will be the same as for CIDP relapse (iRODS), see Sections [8.2.1](#) and [8.2.1.1](#).

The rule for handling missing data is described in Section [4.2.1](#).

Mean change from Baseline in adjusted INCAT score, including 90% CI will be plotted against timepoint for both treatments.

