### **8.2.3 Maximum grip strength as assessed by site personnel and CIDP relapse**

Grip strength is assessed by qualified site personnel each scheduled assessment. Qualified site personnel will be trained regarding obtaining and recording measurements. At each

scheduled visit, the grip strength, generated by the participant, and measured using a standardized tool, will be evaluated 3 times in the dominant hand. All 3 assessments will be recorded in the eCRF. For analyses, UCB will utilize the maximum of the 3 assessments. Efficacy will be assessed as change from Baseline in maximum grip strength score at each scheduled assessment by treatment group during the Treatment and Observation Periods.

CIDP relapse (maximum grip strength as assessed by site personnel) is defined as a clinically important deterioration from Baseline in grip strength as measured by site personnel, ie, a decline of  $>14\text{kPa}$ .

Values and changes from Baseline in maximum grip strength score taken by site personnel will be summarized by treatment group and for all participants and listed by treatment group at each scheduled assessment during the Treatment and Observation Period.

For the change from Baseline in maximum grip strength at each scheduled assessment during the Treatment and Observation Period, treatment differences will be compared using the same MMRM analysis as for the primary endpoint, with the fixed categorical effects of treatment group, assessment week (at pre-specified levels determined by the visit schedule), the treatment by week interaction and the route of administration of prior Ig therapy, as well as continuous fixed covariate of the Baseline value, and participant as a random effect.

Analyses will be performed for the FAS utilizing the observed cases and repeated for the PPS.

Values of grip strength score taken by site personnel will be listed by treatment group. All 3 assessments taken at the scheduled assessments will be listed and the maximum per scheduled assessment will be flagged.

The statistical methods applied to CIDP relapse (maximum grip strength as assessed by site personnel) and time to CIDP relapse (maximum grip strength as assessed by site personnel) will be the same as for CIDP relapse (iRODS), see Sections 8.2.1 and 8.2.1.1. The rule for handling missing data is described in Section 4.2.1.

The analyses on CIDP relapse and time to CIDP relapse will be repeated with a CIDP relapse definition based on a decline of  $>8\text{kPa}$ .

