#### **8.2.4 Patient-reported grip strength**

During the study, participants keep e-diaries to record daily grip strength from the Screening Visit until the end of study participation. Participants should be reminded to bring their diaries with them to each clinic visit and to have them available at home nursing visits. Participants will be trained by the site personnel and receive a manual describing how to assess grip strength using a standardized tool. At approximately the same time every day, the maximum grip strength, the peak pressure generated by the participant, will be assessed 3 times, with at least 30sec between measurements, using the dominant hand. Participants will be asked to complete their diaries each day and record the values for each of the 3 assessments.

For the purpose of the analysis, the mean of the maximum of the 3 daily assessments taken during the last three non-missing days prior to the scheduled visit will be used. Missing data will be handled as described in Section 4.2.1.

Values and changes from Baseline in mean daily maximum grip strength score taken by the participant will be summarized by treatment group and for all participants and listed by

treatment group at each scheduled visit during the Treatment and Observation Period. The treatment differences of change from baseline in the derived grip strength score will be compared using the same MMRM analysis as for the primary endpoint, with the fixed categorical effects of treatment group, assessment week (at pre-specified levels determined by the visit schedule), the treatment by week interaction and the route of administration of prior Ig therapy, as well as continuous fixed covariate of the Baseline value, and participant as a random effect. Analyses will be performed for the FAS utilizing the observed cases and repeated for the PPS.

Values of grip strength score taken by the participant as well as derived scores will be listed by treatment group. All 3 daily assessments taken at the scheduled assessments will be listed and the maximum per scheduled assessment will be flagged.

In addition to the above the daily maximum values will be displayed graphically over time, i.e. each treatment group's mean value and 90% CI of the maximum of the participants' three daily grip strength measurements will be displayed versus the relative day.

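### The primary MMRM pairs a participant random effect with an unstructured visit covariance, where it is redundant, and the non-convergence rule changes the matrix without first dropping that term

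*SAP*

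**What the plan says.** The prose of SAP 8.1.2 lists the fixed effects and then adds "study participant as a random effect, and utilize an unstructured covariance matrix". The SAS PROC MIXED list in the same section treats the components as separate items. Item c reads "The repetition variable is visit", item d reads "Subject ID is set as random factor", and item e refers back to the covariance structure. Protocol 14.3.1 agrees: "The model will define subject as a random effect and utilize an unstructured covariance pattern".

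The rule for a failed fit is: "In case of non-convergence, the model will be fitted using the following covariance matrices until convergence is met". The order is heterogeneous Toeplitz, heterogeneous autoregressive, Toeplitz, autoregressive. Nothing is said about the random effect at any of these steps.

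SAP 8.2.2 extends the model to adjusted INCAT: "at each scheduled assessment during the Treatment and Observation Period, treatment differences will be compared using the same MMRM analysis". SAP 8.2.6 does the same for RT-MRC, and SAP 8.2.3 for site-assessed grip strength: "For the change from Baseline in maximum grip strength at each scheduled assessment during the Treatment and Observation Period, treatment differences will be compared". SAP 8.2.4 also applies the primary model to patient-reported grip strength. Its summary sentence refers to each "treatment group at each scheduled visit during the Treatment and Observation Period", but the visits that enter the model are not listed. All four sections restate participant as a random effect.

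**The concern.** An unstructured matrix leaves every visit variance and every between-visit covariance free. A participant random intercept adds one constant to all of those elements, which the matrix can already absorb. As written, the primary model therefore has one covariance parameter more than the data can determine.

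The consequence lies in the order of steps. If the extra parameter alone caused non-convergence, the SAP would move to heterogeneous Toeplitz, although the unstructured model without that term might have fitted. At 12 visits this means going from 78 free covariance elements to a structure with 24 parameters, participant term included. SAP 8 treats efficacy as exploratory and presents no p-values, so the Week 13 difference and its 90% confidence interval are the primary result. With incomplete data, both depend on the covariance model fitted.

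**Working it through.** **The plan's own figures.** SAP 2.4 gives 15 per group, a one-sided 5% t-test, and effect sizes 0.93 and 0.52. The noncentral t distribution with 28 df gives power of 79.9% and 39.9%, matching the stated 80% and 40%. Evaluable participants: 2 × 15 = 30; 30/(1 − 0.10) = 33.3, rounded up to 34. These figures reproduce and do not depend on the covariance point. The 30 is used below.

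**Visit counts** (Protocol 8.2.3, 8.2.5, 8.2.7, 8.3.1, 8.3.2 and 9.1).
- iRODS to Week 13: Visits 4, 6, 8 to 17 = 12.
- Adjusted INCAT: Visits 4, 6, 8, 10, 12, 14, 16, 17 to 21 = 12.
- Site grip: Visits 4, 6, 8, 10, 12, 14, 16, 17, 19, 21 = 10.
- RT-MRC: Visits 4, 6, 8, 10, 12, 14, 16, 17, 21 = 9.

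**Counting.** An unstructured T-visit matrix has T(T+1)/2 distinct elements; for T = 12, 12 × 13/2 = 78. Adding the participant variance makes 79 parameters for 78 quantities.

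**Exact argument.** Let V be the marginal covariance and J the matrix of ones. For any constant c, V = cJ + (V − cJ). The second part stays positive definite for every c from 0 up to (not including) 1/(1'V⁻¹1). All such splits give the same V and the same likelihood. For homogeneous Toeplitz, V(i,j) = c + t(|i−j|): raising c and lowering every t by the same amount changes nothing.

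**Rank check.** Numerical rank of the derivative of V with respect to all covariance parameters, participant term included:

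| Structure | Visits | Parameters | Rank |
|---|---|---|---|
| Unstructured | 9 | 46 | 45 |
| Unstructured | 10 | 56 | 55 |
| Unstructured | 12 | 79 | 78 |
| Homogeneous Toeplitz | 12 | 13 | 12 |
| Heterogeneous Toeplitz | 12 | 24 | 24 (23 if visit variances are equal) |
| Heterogeneous AR(1) | 12 | 14 | 14 |
| AR(1) | 12 | 3 | 3 |

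If the iRODS model also took in Visits 18 to 21 (an assumption; 16 visits), the unstructured count is 137 with rank 136. For patient-reported grip the visit set is also an assumption: 79/78 for the 12 diary-review visits, 137/136 for 16 visits (without Visits 3, 5 and 7), and 191/190 for all 19.

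**Effect on a converged fit.** Take an assumed 12-visit V with SDs from 0.8 to 1.4 and correlation 0.8^lag. Any participant variance from 0 up to 0.456 gives the same V. With 15 complete participants per group and no covariate adjustment, the standard error of the last-visit difference is √(2 × 1.4²/15) = 0.511 for every split tried (0, 0.114, 0.228, 0.410).

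**Formal rank is not the whole story for heterogeneous Toeplitz.** Under assumed inputs (12 visits, about 30 complete participants, modestly differing visit SDs), the expected-information standard error of the participant variance ran from about 0.7 to about 8 times the variance itself. The result depends on the spread of SDs and the participant share assumed. The term is identified there but may be barely estimable.

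**The case against.** The strongest reply is that item d is loose wording for the subject identifier. Apart from the class list, it is the only item that names the participant, and an unstructured matrix cannot be set up without a blocking unit. That reading is plausible. Against it, the prose of SAP 8.1.2 and Protocol 14.3.1 both say random effect, and items c and d are separate. The text as written gives the redundant model, and removing the random effect resolves the matter under either reading.

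A second reply is that the harm is conditional, and that 78 covariance parameters from about 30 participants are a larger threat to convergence than one redundant parameter. Both parts stand. The pre-specified fallback sequence also limits analyst discretion.

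Three stronger readings are tempting, and the documents do not support them.
- A reader might infer that the primary estimate is biased. It is not: a converged fit has the same V as the plain unstructured model.
- A reader might infer that PROC MIXED will fail, or that a singular Hessian forces the fallback. The documents do not allow failure to be predicted, and the SAP's only stated trigger is non-convergence.
- A reader might infer that removing the term secures the unstructured model. It may still fail.

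**Conclusion.** The point holds in a limited form. As written, the primary model has a participant variance that cannot be identified under the unstructured matrix (79 parameters, rank 78) or under homogeneous Toeplitz (13, rank 12), and four other efficacy models inherit it. This is algebra and needs no assumption about the data; only the visit counts come from the protocol. If the fit converges, the effect on the estimate and standard error is nil. What is at stake is an avoidable move to a more restrictive covariance if the redundant term alone prevents convergence, and the likelihood of that cannot be derived from the documents. In an exploratory pilot this should be corrected before the analysis is programmed, but it does not threaten the conclusions.

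**What to change.** In SAP 8.1.2 (prose and item d), and by reference in 8.2.2, 8.2.3, 8.2.4 and 8.2.6, delete the participant random effect. Name participant as the subject of the repeated specification: `REPEATED visit / SUBJECT=participant TYPE=UN`, keeping Kenward-Roger degrees of freedom. State that the fallback list applies only after this model fails to converge, and say for each fallback whether a random effect is included, with none as the default.

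SAP 3.9 should record the change, because Protocol 14.3.1 names the random effect explicitly and deleting it goes beyond adding detail.

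Under the unstructured and homogeneous Toeplitz matrices the change costs nothing, since the same set of covariance matrices can be fitted. The other three fallbacks lose one parameter each at 12 visits (24 to 23, 14 to 13, 3 to 2) and become slightly more restrictive than as written. If the sponsor wants the term in any of these three, it should say so in advance. Sample size, data collection and trial conduct do not change.

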#### **8.1.2.1 Presentation of primary efficacy variable**

The individual items of the iRODS and overall score will be listed by treatment group and timepoint using the SS. Overall scores will be displayed including raw sum score, logit locations and centile metric scores as well as changes from Baseline in raw sum score, logit locations and centile metric scores. Descriptive summaries will be presented by treatment group and timepoint for both absolute values and changes from Baseline based on the FAS. Raw sum score summary will show only n, median, minimum, maximum. In addition frequencies of raw scores by each iRODS questionnaire item (eating, taking a shower, walking a flight of stairs, standing for hours, etc.) will be calculated.

The summary of the primary MMRM procedure results at each week, i.e. Least Square (LS) Means along with their standard error (SE), LS Mean difference and its 2-sided 90% CI corresponding to the treatment group difference at each week, will also be presented in the descriptive statistics for raw sum score, logit location and centile metric score.

Mean change from Baseline including 90% CI of the centile metric score will be plotted against timepoint for both treatments.

#### **8.1.3 Supportive and sensitivity analyses of the primary efficacy variable**

Different sensitivity analyses to evaluate the effect of missing observations on the primary analysis findings will be performed. This applies to summary of observed results and MMRM for iRODS.

##### **8.1.3.1 Per-protocol analysis**

The first supportive analysis will be performed in the same way as the primary analysis, using the PPS.

##### **8.1.3.2 LOCF**

A further analysis will utilize the LOCF approach; a missing value will be replaced by the most recent previously observed post-Baseline value of the variable up to day 85 and the analysis will be performed for the FAS. In case a participant discontinues the study prematurely, the assessment of the PEOT visit will be mapped to next missing visit according to the visit schedule utilizing the relative day in study to a maximum of day 85 (Visit 17) before applying LOCF.

##### **8.1.3.3 MFAS**

In addition, a further exploratory sensitivity analysis to ensure the robustness of the results in relation to dose variation will be conducted for the primary endpoint, using the MFAS.

## 8.2 Statistical analysis of the other efficacy variables

### 8.2.1 CIDP relapse, MMRM and summary tables will be performed on the FAS and repeated for the PPS for iRODS, adjusted INCAT and clinician reported grip strength.CIDP relapse (iRODS)

CIDP relapse (iRODS) is defined as a clinically important deterioration from Baseline in iRODS score, i.e. a standardized change from baseline smaller than or equal to the minimum clinically important differences-standard error (MCID-SE) of  $\leq -1.96$ .

This standardized change from baseline refers to individual person-level responsiveness calculated by individual change divided by their corresponding SE of difference at a given timepoint. [Va15]

$$\text{"MCID - SE"} = \frac{\text{Standardized value}_{\text{Visit}} - \text{Standardized value}_{\text{Baseline}}}{\sqrt{\text{SE}_{\text{Visit}}^2 + \text{SE}_{\text{Baseline}}^2}}$$

Values and changes from Baseline in iRODS scores will be summarized by treatment group and for all participants and listed by treatment group at each scheduled assessment during the Treatment and Observation Period.

The point estimate and the corresponding 2-sided 90% CI for the difference between placebo and rozimab CIDP relapse rates up to week 13 will be reported. The CI will be constructed using the asymptotic standard error (asymptotic Wald confidence limits).

Analyses will be performed for the FAS utilizing the observed cases.

Sensitivity analysis for relapse will be performed in the same way, however for the PPS.

The rule for handling missing data is described in Section 4.2.1.

